9.1.2 Timing of response assessment

For timing of response assessment for patients who have discontinued IT treatment due to toxicity, please refer to [Appendix 2](#).

The response assessments will be performed after C2, C4, C8, C13, and EOT. All response assessments (except EOT) should be performed before D1 of next cycle.

In addition, for patients who achieve:

- a first CR or PR after C4 *OR*
- a first CR or PR after C8

a confirmatory response assessment should be performed within 4-6 weeks after detection of the overall response.

If the patient discontinue treatment due to PD, response assessment at EOT is not required provided that PD is documented by scan and/or biopsy.

For patients who have not experienced PD or started new anti-cancer treatment, response assessment should be performed at approximately every 4 months after EOT during long-term FU (see Section [3](#)).

9.2 Safety Assessment

9.2.1 Physical Examination

The physical examination should include an assessment of general appearance and a review of systems (dermatologic, head, eyes (incl examination for mydriasis, signs/symptoms of blurred/altered vision), ears, nose, mouth/throat/neck, thyroid, lymph nodes, and respiratory, cardiovascular, gastrointestinal, extremities, musculoskeletal, neurologic systems). A physical examination should be performed at screening, prior to first treatment with IMP in each cycle, at EOT and otherwise as clinically indicated.

9.2.2 Vital Signs

Vital sign measurements must include heart rate, respiratory rate, body temperature and BP. Additionally, peripheral oxygen saturation (SpO₂) must be measured when clinically indicated. Temperature must be measured by using the same method (e.g., ear thermometer) each time. Vital signs must be assessed at screening and in connection with each treatment cycle as outlined below:

On Days 1, 3 and 5 prior to administration of temozolomide.

On naxitamab in fusion days (Days 2, 4, 8 and 10)

- Prior to administration of temozolomide (Days 2 and 4)
- Prior to pre-medication (e.g., hydromorphone or morphine)
- Prior to start of naxitamab infusion
- ~15 min after start of naxitamab infusion
- ~30 min after start of naxitamab infusion
- Prior to each hydromorphone or morphine IV therapy as feasible (no temperature)
- At completion of naxitamab infusion including flush (no temperature)

- ~15 min after completion of the flush (no temperature)
- Every hour while patient is recovering in the outpatient clinic

Furthermore, vital signs must be assessed at EOT and as clinically indicated. The latter includes when a vital sign parameter is part of an AE on an infusion day.

Please refer to [Appendix 2](#) for patients who have discontinued IT treatment due to toxicity.

9.2.3 Naxitamab Discharge Criteria

Vital signs should be stable and satisfactory at the discretion of the investigator. A minimum of 2 hours after completion of naxitamab treatment, **or** 2 hours after the last dose of any IV opioid must have elapsed.

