21. Allogeneic hematopoietic stem cell transplantation (allo-SCT) or donor-lymphocyte-infusion (defined as any kind of active allogeneic lymphocyte suspension)
 - a. within 6 months of 1st dose of GM-CSF or
 - b. with a lymphocyte count $< 0.2 \times 10^9/L$
22. Treatment with Hematopoietic Progenitor Cell (HPC) boost within 2 months prior to enrollment
23. History of allergy or known hypersensitivity to GM-CSF, yeast-derived products, or any component of GM-CSF, naxitamab, irinotecan or temozolomide
24. History of anaphylactic reactions CTCAE Grade 4 related to prior anti-GD2 antibody therapy
25. Unacceptable hematological status at screening (hematological support is allowed if administered ≥ 1 week before screening procedure), defined as one of the following:
 - a. Hemoglobin $< 5.0 \text{ mmol/L} (< 8 \text{ g/dL})$
 - b. White blood cell count $< 1000/\mu\text{L}$
 - c. Absolute neutrophil count $< 750/\mu\text{L}$
 - d. Platelet count $< 75,000/\mu\text{L}$
26. Unacceptable liver function at screening, defined as one of the following:
 - a. Alanine aminotransferase (ALT) and aspartate aminotransferase (AST) > 5 times upper normal limit (UNL)
 - b. Total bilirubin $> 1.5 \times \text{UNL}$
27. Unacceptable kidney function at screening, defined as:
 - Estimated glomerular filtration rate (eGFR) $< 60 \text{ mL/min}/1.73 \text{ m}^2$ calculated by the 2009 revised Bedside Schwartz Equation ([Appendix 1](#))
28. Inability to comply with protocol
29. Patients with a significant intercurrent illness (any ongoing serious medical problem unrelated to cancer or its treatment) that is not covered by the detailed exclusion criteria and that is expected to interfere with the action of IMPs or to significantly increase the severity of the toxicities experienced from trial treatment
30. Females of childbearing potential (as defined in Section [9.2.8](#)) who are pregnant, breast feeding, intend to become pregnant, or are not using adequate contraceptive methods as defined in [9.2.8](#) or males who are not using adequate contraceptive methods as defined in [9.2.8](#). Contraception must be used for 6 months after last IT treatment or 42 days after last naxitamab treatment whichever comes last for both genders

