8.1.2.3 Naxitamab

On days when co-administered with GM-CSF, naxitamab infusion is started ≥ 60 min after GM-CSF.

On days when co-administered with IT (i.e., Days 2 and 4), it is recommended to start naxitamab infusion at least 1 hour after irinotecan administration to allow for preparations and administration of pre-medications.

Naxitamab should be infused IV at 2.25 mg/kg/day on Days 2, 4, 8 and 10 for a total dose of 9 mg/kg per cycle (Please refer to Appendix 2 for details on naxitamab treatment if the patient has discontinued IT treatment due to toxicity). Administration of naxitamab should be adjusted according to Section 8.4.5, if selected naxitamab adverse reactions are observed. If any events occur fulfilling a general discontinuation criterion the patient must be withdrawn from all treatments immediately and enter long-term FU, see Section 7.12.

At Cycle 1 Day 2 (C1D2):

Naxitamab should be infused over approximately 60 min.

All subsequent naxitamab infusions:

Naxitamab should be infused over approximately 30 min.

Special circumstances

The infusion may be given over approximately 60 min. at Day 2 of any cycle at the investigator's discretion if:

- The patient during C1D2 experienced naxitamab related hypotension:
 - Grade 4 **or**
 - Grade 3 not adequately responding to intervention
- At the investigator's discretion due to severe infusion related adverse drug reactions not adequately responding to interventions

The 60/30 min infusion time is a minimum infusion time. If infusion pause or infusion rate reduction is required due to infusion related AE (see Section [8.4.5](#)) the infusion time will become longer.

Naxitamab treatment in an out-patient setting is defined as a naxitamab infusion performed in the ambulatory setting.

In-patient treatment (i.e. requiring hospitalization) includes both short term admissions and admissions requiring overnight stay.

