8.4.1 Pre-medications Prior to Naxitamab Infusions

Pre-medication is needed to mitigate expected AEs with naxitamab. These include pain, infusion-related reactions, hypotension, allergic reactions, nausea/vomiting and potentially anxiety.

Infusion with naxitamab is associated with pain that may be severe. The pain may involve the abdomen, lower back, chest, legs and arms. The duration may vary but, for most patients, the pain lasts for a couple of hours, and tends to be worst during the naxitamab infusion, subsiding approximately 15 min after end of infusion. Due to the pain, patients may “hold their breath”. A marked variation in the naxitamab-associated pain may be observed from infusion to infusion, and hence the recommended opioid dosages below are applicable only to the first infusion. Opioid pre-medications for mitigation of pain during subsequent infusions of naxitamab and pain medications after completion of the naxitamab infusion should be adjusted at the discretion of the investigator.

All medications (including opioid usage) should be captured on the concomitant medication eCRF.

At home

To reduce the risk of pain, gabapentin should be administered from Day -3 to Day 12 of each cycle according to local SoC (e.g., dose of 5 to 10 mg/kg with a max dose of 600 mg).

It is recommended to titrate to the final effective dose during the first 3 days of treatment:

Day -3: Once daily; Day -2: Twice daily; Day -1 and until Day 10: 3 daily doses (please refer to [Appendix 2](#) if the patient has discontinued IT treatment due to toxicity).

After completion of the naxitamab treatment (i.e. Day 10), it is recommended to taper off the gabapentin treatment: Day 11: Twice daily; Day 12: Once daily. If nerve pain lingers, the patient may continue gabapentin on twice daily dosing for up to a week post naxitamab treatment before further weaning.

At hospital

- Saline solution 0.9% (to reduce risk of severe hypotension)
 - Patients should be preloaded with saline 0.9% infusion 10mL/kg over 1 hour just prior to the start of all naxitamab infusions
- Opioids
 - Per os (PO) opioids are preferred over IV to diminish IV related side effect such as hypotension, respiratory depression, and/or decreased responsiveness
 - Oxycodone 0.1 – 0.2 mg/kg with a max dose of 5 mg PO (45 – 60 min before naxitamab infusion) **or** equivalent dose of PO opioids **or**

- In cases where PO administration is not feasible (15 min before naxitamab infusion):

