8.4.2 Supportive therapy to be readily available during naxitamab

The following supportive therapies should be readily available at the bedside as pre-prepared treatments when the naxitamab infusion is initiated

- For use at the onset of pain (pre-charged syringes):
 - Hydromorphone 0.00375 – 0.015 mg/kg given IV over 1 – 5 min, **or**
 - Morphine sulfate/ Morphine Sodium Chloride 0.025 – 0.1 mg/kg given IV over 1 – 5 min.
 - Opiate doses may be repeated every 5 min for a total of 4 doses. The low, but frequent intermittent doses are preferred to mitigate the risk of opioid associated hypotension.
 - Additional doses may be ordered and given PRN at the discretion of the treating physician
- PRN:
 - Lorazepam 0.01-0.02 mg/kg PO or IV (max 1 mg) or equivalent according to local SoC
 - H1 receptor blocker according to local SoC (e.g., dexclorfeniramine at 0.15 mg/kg IV (max 5 mg) or diphenhydramine for IV administration)
 - NSAID according to local SoC
 - Methylprednisolone 2 mg/kg IV with a max dose of 80 mg (in case corticosteroid was not given as pre-medication) **or** equivalent corticosteroid dose. If corticosteroid was administered as pre-medication, a dose reduction should be considered at the investigator's discretion
 - Adrenalin (epinephrine) 0.01 mg/kg IV or IM (max 0.5 mg)
 - Selective beta2-adrenergic receptor agonist nebulized administered PRN according to local SoC (e.g., salbutamol < 20 kg: 2.5 mg; >20 kg: 5 mg) for bronchospasm
 - Epinephrine for inhalation PRN for stridor
 - Naloxone IV 1 mcg/kg/doses (to be repeated every 2-3 min until response) for management of potential acute cases of respiratory depression:
 - Saline 0.9% for bolus infusion: 10-20 mL/kg IV according to Section [8.4.5.2](#)
 - Cold and hot pads to be applied locally in any body area ad libitum as part of pain management
 - Oxygen (oxygen mask and humidified oxygen inhalation equipment must be available)

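### The discharge rule joins two 2-hour clocks with a bare 'or', so after an IV opioid neither 2-hour interval is assured

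*Combined protocol and SAP*

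**What the plan says.** Section 9.2.3 asks for stable, satisfactory vital signs in the investigator's judgement and then sets the time rule: "A minimum of 2 hours after completion of naxitamab treatment, or 2 hours after the last dose of any IV opioid must have elapsed". Appendix 2 refers back to this section for the naxitamab + GM-CSF alone regimen and adds nothing on timing.

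Opioid use is described in two places.

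- Section 8.4.1 favours the oral route: "Per os (PO) opioids are preferred over IV to diminish IV related side effect such as hypotension, respiratory depression, and/or decreased responsiveness". If oral dosing cannot be used, IV hydromorphone or morphine is given 15 minutes before the infusion. On later analgesia it says that "pain medications after completion of the naxitamab infusion should be adjusted at the discretion of the investigator".
- Section 8.4.2 requires IV opioid syringes at the bedside for the onset of pain. "Opiate doses may be repeated every 5 min for a total of 4 doses", and the treating physician may order more as needed.

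Section 8.1.2.3 sets infusions at about 60 minutes for Cycle 1 Day 2 and about 30 minutes afterwards, both as minimum times. It also provides that "The infusion may be given over approximately 60 min. at Day 2 of any cycle". That option is for patients with Grade 4 hypotension, or Grade 3 hypotension responding poorly, at Cycle 1 Day 2, and for severe infusion reactions that do not respond adequately.

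**The concern.** A rule that offers two conditions joined by 'or' is met when the first of them is met. Each clock guards against a different hazard: one covers reactions to naxitamab, the other the effects of the IV opioid. Letting either stand in for the other means that only the clock that runs out first is certain to be respected.

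The hazards are ones the protocol names. Section 8.4.1 gives hypotension, respiratory depression and reduced responsiveness as its reasons for avoiding the IV route. Section 4.3.2 lists hypotension, bronchospasm, stridor and depressed consciousness among the Grade 3 or higher events seen in at least 10% of patients in at least one earlier naxitamab trial. It also reports that 95% of infusions in Trial 201 were given to outpatients, so discharge is a routine step. Patients may be as young as 12 months.

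Elsewhere the protocol says which of two competing intervals governs. Exclusion criterion 30 in Section 7.11.2 sets contraception at 6 months after the last irinotecan/temozolomide dose or "42 days after last naxitamab treatment whichever comes last for both genders". Section 9.2.8 does the same, and Section 10.8 names the earlier time where that is what it wants. Section 9.2.3 has no such phrase.

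**Working it through.** The plan states no figure to reproduce. The check is timeline arithmetic.

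**Inputs**

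- Both clocks: 120 min (Section 9.2.3).
- IV pre-medication: 15 min before the start of infusion (Section 8.4.1).
- Infusion length: 30 or 60 min (Section 8.1.2.3).
- Repeat dosing: 4 doses at 5-min intervals (Section 8.4.2), so the last dose is 15 min after the first.
- Assumed: a last dose midway through the infusion; a 4-dose course begun at the end of infusion; single last doses 30 and 60 min after it.

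**Formulas.** Let *t* be the time of the last IV opioid in minutes from the end of infusion (negative if before it).

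- Literal reading, −120 < *t* ≤ 0: the opioid clock runs out first, and the rule is met 120 + *t* min after naxitamab.
- Literal reading, 0 < *t* < 120: the naxitamab clock runs out first, and the rule is met 120 − *t* min after the opioid.
- Later-of-two reading: the rule is met max(120, 120 + *t*) min after naxitamab.
- Extra stay under the later-of-two reading: |*t*| min.

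For pre-medication only, *t* = −(15 + 30) = −45 with a 30-min infusion and −(15 + 60) = −75 with a 60-min infusion.

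| Last IV opioid | *t* | Literal: min after naxitamab | Literal: min after opioid | Later of two: min after naxitamab | Later of two: min after opioid | Extra stay (min) |
|---|---|---|---|---|---|---|
| Pre-medication only, 30-min infusion | −45 | **75** | 120 | 120 | 165 | 45 |
| Pre-medication only, 60-min infusion | −75 | **45** | 120 | 120 | 195 | 75 |
| Midway, 30-min infusion (assumed) | −15 | **105** | 120 | 120 | 135 | 15 |
| Midway, 60-min infusion (assumed) | −30 | **90** | 120 | 120 | 150 | 30 |
| At end of infusion | 0 | 120 | 120 | 120 | 120 | 0 |
| 4-dose course begun at end (assumed) | 15 | 120 | **105** | 135 | 120 | 15 |
| 30 min after end (assumed) | 30 | 120 | **90** | 150 | 120 | 30 |
| 60 min after end (assumed) | 60 | 120 | **60** | 180 | 120 | 60 |

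Bold marks an interval below 120 min. With no IV opioid, only the naxitamab clock exists and the full 120 min stands.

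In each literal row at least one interval reaches 120 min, and in every row except *t* = 0 the other falls short. Under the later-of-two reading both reach 120 min in every row. Pauses or rate cuts lengthen the infusion and so widen the pre-medication shortfall beyond the figures shown.

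**The case against.** The strongest reply is that this is loose drafting with an obvious intent. The rule is phrased as a minimum, and the opioid clause reads naturally as an added condition for patients given an IV opioid. Nothing shows that any site applies the earlier clock. That is fair as to intent. But a site that simply switches to the opioid clock whenever an IV opioid was given still leaves the interval after naxitamab uncovered if the last dose came before the end of infusion.

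A second reply is that discharge never rests on the clock alone. Vital signs must be satisfactory. Section 9.2.2 schedules them at completion, about 15 minutes after the flush and then hourly. Section 9.2.7 schedules pain scores about 15 and 30 minutes after the infusion and again before discharge. This stands in part: following the schedule implies about 30 minutes of observation. That is shorter than every interval in the table, and it does nothing for the interval after a late opioid dose.

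A third reply is that the largest shortfalls need an uncommon path: oral dosing not feasible, IV pre-medication given, and no IV rescue later, although Section 8.4.1 says the pain "tends to be worst during the naxitamab infusion, subsiding approximately 15 min after end of infusion". The same sentence makes very late doses unlikely, and the post-infusion text in that section does not name IV opioids. These points bear on frequency, which the documents do not give. They do not change what the rule permits.

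**Conclusion.** The concern holds. When an IV opioid is given at any time other than the end of infusion, the literal rule lets one of the two 2-hour intervals be cut short by the gap between the last dose and the end of infusion. From the protocol's own timings, the shortfall after naxitamab is 45 minutes for a 30-minute infusion and 75 minutes for a 60-minute infusion when the only IV opioid is pre-medication. The 60-minute case includes every patient's first exposure and, at the investigator's discretion, later Day 2 infusions in patients who had serious hypotension or severe infusion reactions. The mid-infusion and post-infusion figures rest on the assumed dose times.

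This is a safety-wording defect that should be corrected. It is confined to patients given IV opioids and is softened by the scheduled checks. It has no bearing on the primary analysis.

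**What to change.** Reword Section 9.2.3 along these lines: discharge is allowed no sooner than 2 hours after naxitamab has finished and, where any IV opioid was given, no sooner than 2 hours after its last dose; the later of the two times applies. Appendix 2 points to this section, so the naxitamab + GM-CSF alone regimen is covered without a separate edit.

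The cost is one sentence in an amendment, with the submission and approval that Section 14.3 requires before changes take effect, and a notice to sites. Compared with the literal reading, a patient given an IV opioid stays longer by the amount in the last column of the table. Patients given none stay no longer, and sites that already apply the later clock would see no change.

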9.2.4 Echocardiography

An echocardiography should be performed at screening (refer to Section 3). The investigator should make an overall interpretation and assess for trial eligibility.

9.2.5 Pulmonary Function Test and Oxygen Saturation

A pulmonary function test and oxygen saturation should be performed at screening, if clinically indicated. The investigator should make an overall interpretation of the pulmonary function test(s) and oxygen saturation and assess for trial eligibility.

9.2.6 ECG

12-lead ECG should be obtained as outlined in the flow chart (see Section 3) using an ECG machine that automatically calculates the heart rate and measures PR, QRS, QT, and QTc intervals.

ECG is a local assessment at screening, and at EOT. If the patient needs sedation before ECG, the ECG can be performed in connection with imaging. The investigator should make an overall interpretation of the ECG and at screening assess for trial eligibility.

9.2.7 Pain Assessment

Pain scores should be assessed for all naxitamab infusions and at the following time points:

- Prior to start of naxitamab
- Worst pain during infusion; to be assessed at the end of infusion
- ~ 15 min after end of infusion
- ~ 30 min after end of infusion
- Prior to discharge

The same scale must be used during all naxitamab infusions, also if the patient turns 6 years during the trial. The Face, Legs, Arms, Cry, Consolability (FLACC) scale for patients \leq 5 years old at screening and Wong-Baker FACES® pain scale for patients 6 years or older at screening.

If patients of at least 6 years of age cannot comply with the Wrong-Baker faces pain scale it is permitted to use the FLACC scale at the investigators discretion as long as it is used consistently throughout all naxitamab infusions. Please refer to [Appendix 8](#) and [Appendix 9](#).

9.2.8 Non-child-bearing Potential/Pregnancy Test

Pregnancy testing and contraceptive requirements do not apply for female patients of non-child-bearing potential. Non-child-bearing potential in female patients will be confirmed by one of the following:

- Females who have not reached menarche or
- Females who have not had menses within the past 12 months and have a follicle-stimulating hormone (FSH) ≥ 40 IU/L or
- Females who have not had menses within the past 24 consecutive months if a FSH measurement is not available or
- Females who have undergone surgical sterilization (e.g., hysterectomy, or bilateral oophorectomy, or bilateral salpingectomy).

Pregnancy and contraceptive requirements for female patients of child-bearing potential

Women of child-bearing potential (WOCBP) must have a negative serum pregnancy test at screening and are excluded from the trial if they do not agree to use highly effective contraception for a period of 6 months after the last treatment with IT or 42 days after last treatment with naxitamab whichever comes last. Highly effective contraceptive methods can achieve a failure rate of less than 1% per year when used consistently and correctly. Such methods include:

- combined (estrogen and progestogen containing) hormonal contraception associated with inhibition of ovulation:
 - oral
 - intravaginal
 - transdermal
- progestogen-only hormonal contraception associated with inhibition of ovulation:
 - oral
 - injectable
 - implantable
- intrauterine device (IUD)
- intrauterine hormone-releasing system (IUS)
- bilateral tubal occlusion
- vasectomised partner¹
- sexual abstinence²

¹ Vasectomised partner is a highly effective birth control method provided that partner is the sole sexual partner of the female patient and that the vasectomised partner has received medical assessment of the surgical success.

² Sexual abstinence is considered a highly effective method only if defined as refraining from heterosexual intercourse during the entire period of risk associated with the study treatments. The reliability of sexual abstinence needs to be evaluated in relation to the duration of the clinical trial and the preferred and usual lifestyle of the patient.

If a patient is assessed to be of child-bearing potential, either at screening or become so during the course of the trial, a serum pregnancy test must be performed prior to each treatment cycle and at EOT.

Contraceptive requirements for male patients

Male patients must use contraception (condom) for a period of 6 months after last treatment with IT or 42 days after last treatment with naxitamab whichever comes last. Male partners for female patients are advised to use condom while the female partner is being treated with IT and for 2 weeks after last treatment.

